5.5.3. Dose Adjustment for Hematologic Toxicity

The dose of azacitidine and/or GSK2879552 may be adjusted based on neutrophil, platelet, WBC and bone marrow biopsy cellularity at baseline and nadir according to the guidelines below:

No dose adjustments are needed for anemia.

For patients with baseline (start of treatment) $WBC \geq 3.0 \times 10^9/L$, $ANC \geq 1.5 \times 10^9/L$, and platelets $\geq 75.0 \times 10^9/L$, adjust the dose as follows, based on nadir counts for any given cycle:

| Nadir Counts | | % Dose of Azacitidine/GSK2879552 to be administered |
|---------------------------|---------------------------------|---|
| Course | | - |
| ANC (x10 ⁹ /L) | Platelets (x10 ⁹ /L) | |
| <0.5 | <25.0 | 50%/50-67% |
| 0.5 –1.5 | 25.0-50.0 | 67%/67-100% |
| >1.5 | >50.0 | 100%/100% |

For patients whose baseline counts are $WBC < 3.0 \times 10^9/L$, $ANC < 1.5 \times 10^9/L$, or platelets $< 75.0 \times 10^9/L$, dose adjustments should be based on nadir counts and bone marrow biopsy cellularity at the time of the nadir as noted below, unless there is clear improvement in differentiation (percentage of mature granulocytes is higher and ANC is higher than at onset of that course) at the time of the next cycle, in which case the dose of the current treatment should be continued.

| WBC or Platelet Nadir % decrease in counts from baseline | Bone Marrow Biopsy Cellularity at Time of Nadir (%) | | |
|--|---|------------|------------|
| | 30-60 | 15-30 | <15 |
| % Dose of Azacitidine/GSK2879552 to be administered - | | | |
| 50 - 75 | 100%/100% | 50%/33-67% | 33%/25-50% |
| >75 | 75%/50-100% | 50/33-67% | 33%/25-50% |

If a nadir as defined in the table above has occurred, the next course of treatment should be given 28 days after the start of the preceding course, provided that both the WBC and the platelet counts are >25% above the nadir and rising. If a >25% increase above the nadir is not seen by day 28, counts should be reassessed every 7 days. If a 25% increase is not seen by day 42, then the patient should be treated with 50% of the scheduled dose.

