4.7. Permanent Discontinuation of Study Treatment

Subjects will receive study treatment until disease progression (according to IWG), death, withdrawal of consent, or unacceptable toxicity, including meeting stopping criteria for liver chemistry. The investigator may discuss with a GSK Medical Monitor continuing a subject who is receiving clinical benefit but has met the formal criteria for disease progression, if the following criteria are met: Investigator-determined clinical benefit (e.g. symptomatic improvement), lack of significant toxicity (no drug related non-

hematologic grade 3/4 AEs within the last 4 weeks) and no therapeutic alternatives expected to provide durable responses.

In addition, study treatment may be permanently discontinued for any of the following reasons:

- Substantial deviation(s) from the protocol
- Request of the subject or proxy (withdrawal of consent by subject or proxy)
- Investigator's discretion
- A clinically significant adverse event leading to an interruption of treatment for greater than 14 days. If the investigator and GSK Medical Monitor conclude that the benefit: risk is positive and supports continued treatment in a subject who has had a > 14 day treatment delay, then the subject may continue therapy with the approval of the GSK Medical Monitor on case by case basis.
- Persistent G4 thrombocytopenia for >4 weeks not attributed to disease or requires platelet transfusions for bleeding in the absence of the disease
- Intercurrent illness that prevents further administration of study treatment(s)
- Subject is lost to follow-up.
- Study is closed or terminated.

Once a subject has permanently discontinued study treatment, the subject will not be allowed to re-enter this study. All subjects who discontinue from study treatment will have safety assessments at the time of discontinuation and during post-study treatment monthly follow-up.

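### The day-42 haematologic dose rule names neither its reference dose nor its drug, so at marrow cellularity below 15% it yields two azacitidine doses three-fold apart, one of them above the dose given after recovery

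*Protocol*

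**What the plan says.** Protocol Section 5.5.3 has two dose tables. The second covers subjects who start with a low WBC, ANC or platelet count. It assigns azacitidine and GSK2879552 percentages (in that order) by the percentage fall in counts and by marrow cellularity at nadir, in columns of 30–60, 15–30 and below 15. The row for a fall of 50–75% reads "50 - 75 | 100%/100% | 50%/33-67% | 33%/25-50". The row for a larger fall reads ">75 | 75%/50-100% | 50/33-67% | 33%/25-50" (all entries are percentages). The table dose applies "unless there is clear improvement in differentiation", in which case the current dose is kept.

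The paragraph directly below deals with timing. When a nadir of the kind in the preceding table has occurred, it places the next course on day 28, counted from when its predecessor began, under one condition: "provided that both the WBC and the platelet counts are >25% above the nadir and rising". Failing that, counts are rechecked weekly. The last sentence is: "If a 25% increase is not seen by day 42, then the patient should be treated with 50% of the scheduled dose".

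The term *scheduled dose* is not defined in this section, and the sentence names no drug. The planned azacitidine dose is 75 mg/m² on Days 1–7 (Sections 4.2 and 4.10.2).

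**The concern.** The closing sentence tells a site what to give a subject whose counts have not come back. It follows a table that has already set a reduced percentage for each drug separately. *Scheduled dose* can then mean two things: the full planned dose, or the dose the table has just scheduled for the next course. Nothing nearby settles it.

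The only other relevant use of the term is in the DLT-evaluability rules (Sections 4.3.1 to 4.3.3), where it counts doses taken in the first four weeks. It is not a definition for dose reduction. Section 5.5.2, by contrast, names its target when it sets a reduction: azacitidine for the bicarbonate rule, both drugs for late-resolving non-haematologic toxicity. The day-42 sentence does neither.

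At stake is whether a subject in this position has one dose or several. On one reading, in the most hypocellular column, a subject without count recovery would receive more azacitidine in the next course than the same subject with recovery. Two sites following the text in good faith could also give the same subject quite different doses.

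**Working it through.** **Inputs**, all from the Protocol:
- Planned azacitidine dose: 75 mg/m² (Section 4.10.2).
- Table percentages by cellularity column 30–60 / 15–30 / <15 (Section 5.5.3, second table). Azacitidine: 100 / 50 / 33 for a fall of 50–75%, and 75 / 50 / 33 for a fall above 75%. GSK2879552: 100 / 33–67 / 25–50, and 50–100 / 33–67 / 25–50.
- Day-42 factor: 50% (Section 5.5.3, last sentence).

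**Formulas**
- After recovery: table %.
- Day 42, full-dose reading: 50% of the planned dose.
- Day 42, table-dose reading: 0.5 × table %.
- Ratio of the two day-42 readings: 50 ÷ (0.5 × table %).

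**Azacitidine (mg/m² on a base of 75)**

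| Fall in counts | Cellularity | After recovery | Day 42, full-dose reading | Day 42, table-dose reading | Ratio of readings |
|---|---|---|---|---|---|
| 50–75% | 30–60 | 100% = 75 | 50% = 37.5 | 50% = 37.5 | 1.0 |
| >75% | 30–60 | 75% = 56.25 | 50% = 37.5 | 37.5% = 28.1 | 1.33 |
| either | 15–30 | 50% = 37.5 | 50% = 37.5 | 25% = 18.75 | 2.0 |
| either | <15 | 33% = 24.75 | 50% = 37.5 | 16.5% = 12.4 | 3.03 |

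In the <15 column the full-dose reading is 50 ÷ 33 = 1.52 times the dose after recovery, and the table-dose reading is half of it. In the other columns the full-dose reading is equal to the table dose (15–30) or below it (30–60). The reversal therefore occurs in 2 of the 6 table cells, both in the <15 column, and only on the full-dose reading.

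**GSK2879552, if the sentence covers it**
- <15: the table gives 25–50%. The full-dose reading is 50%, at or above that range. The table-dose reading is 12.5–25%. The ratio runs from 50 ÷ 25 = 2 to 50 ÷ 12.5 = 4.
- 15–30: the table gives 33–67%. The table-dose reading is 16.5–33.5%, and the ratio runs from 1.49 to 3.03.

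**Two checks on scope**
- The paragraph refers to the table above it, and the cellularity table stands directly above. If the first table (baseline counts not low) were also meant, its azacitidine doses of 50, 67 and 100% would give ratios of 2.0, 1.49 and 1.0, with no reversal.
- Per unit time the reversal largely disappears. A 50% course started at day 42 instead of day 28 amounts to 50 × 28 ÷ 42 = 33.3% per 28 days for that interval, about the same as 33% given on time.

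**The case against.** The strongest reply is that this is a narrow corner of a guideline. The section says doses may be adjusted, its GSK2879552 entries are ranges, and some variation between sites is built in. To reach the reversal a subject needs a low baseline count, a fall of at least 50%, cellularity below 15% at nadir, no 25% rise by day 42, and no clear improvement in differentiation. On-study marrow is done only as clinically indicated (Section 7.1), and Arm A subjects receive no azacitidine before crossover. All of this stands and limits how often the problem can arise. It does not supply the missing reference dose or drug. A range written into a table is a deliberate choice, whereas an undefined base is not.

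It can also be said that the section opens by referring to azacitidine and/or GSK2879552, so context supplies the drug. But that wording leaves open which of them the day-42 sentence means.

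Several stronger readings are tempting and are not supported:

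- **That non-recovery always earns a higher dose, and that the dose is also ambiguous three-fold.** The reversal needs the full-dose reading; on the other reading the dose is half the table dose. These are alternatives, and the three-fold figure belongs to azacitidine in the <15 column only. The reversal is also per course, not per unit time.
- **That the rule conflicts with Section 4.7.** That section lists "A clinically significant adverse event leading to an interruption of treatment for greater than 14 days" as a reason for which treatment may be stopped, and allows continuation with Medical Monitor approval. Day 42 is 42 − 28 = 14 days after the planned start, so a course given then is not beyond 14 days. A delayed course also need not follow from a clinically significant adverse event.
- **That many subjects are affected, or that the response data are.** The eligibility criteria admit subjects with low counts, so the table may apply widely. But the Protocol gives no frequency for the combination of conditions above, and no path to the clinical benefit rate or to a decision rule is shown.

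**Conclusion.** The point holds in a limited form. The day-42 sentence is an instruction that sites must carry out, with an undefined base and no named drug. At cellularity below 15% it yields azacitidine at 37.5 or 12.4 mg/m², three-fold apart, against 24.75 mg/m² after recovery; the higher figure exceeds the recovered dose for that course. At 15–30% the readings are two-fold apart, and at 30–60% 1.0- to 1.33-fold, without a reversal. For GSK2879552 below 15% they are 2- to 4-fold apart if the sentence covers that drug.

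These figures assume a base of 75 mg/m², that the cellularity table is the one referred to, and that the differentiation exception does not apply. They say nothing about how often the case arises. Because one plausible reading reverses the direction of the reduction, this is a defect in the rule and more than a missing detail. No conclusion is drawn on which dose is right.

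**What to change.** The sponsor should reconcile the last sentence of Section 5.5.3 with the cellularity table above it. The revised text should:

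- define the reference dose for *scheduled dose*, saying whether it is the full planned dose or the dose assigned by the table;
- name the drug or drugs the sentence covers, including what it means for a subject on GSK2879552 alone;
- be checked against every cell of the table, so that each combination of nadir, cellularity and recovery leads to one determinate rule and any dose above the recovered-subject dose is there by intent.

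The choice of dose is a clinical one for the sponsor. The cost is an edit to one section, with no new data, no change to the assessment schedule and no effect on sample size.

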5.6. Subject and Study Completion

A subject will be considered to have completed the study if they are followed until death.

Subjects who have not died, and are no longer being followed for survival are considered to have discontinued the study. The End of Study eCRF should only be completed when a subject is no longer being followed.

The study will be considered completed for the purpose of a final analysis when 70% of subjects enrolled in Part 2 have progressed or died. If available, subjects continuing on treatment at the time of final analysis may be offered the option to continue in a rollover trial.

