2.2.6. Azacitidine

Azacitidine (5-azacitidine, 5-aza, Vidaza) is a pyrimidine nucleoside analog of cytidine, which causes hypomethylation (demethylation) of DNA and has direct cytotoxicity on abnormal bone marrow hematopoietic cells. It is approved for the treatment of patients with MDS in the US. Available studies indicate overall response rates in patients with low or intermediate-1 risk MDS of approximately 50 percent, with survival benefits observed in responders versus nonresponders. In most centers azacitidine is administered in an outpatient setting at a dose of 75mg/m² per day subcutaneously for 7 consecutive days every 28 days. Best responses may not occur until six cycles have been given. In the combined the Cancer and Leukemia Group B (CALGB) experience, the median number of cycles to first response was three, with 90 percent of responses seen by cycle six. More convenient dosing regimens, in which the agent is given for only five consecutive days, or with a "drug holiday" over the weekend, or as a 10-day cycle have also been adopted by clinicians. Dose adjustment and growth factor support are necessary for some patients during treatment with azacitidine.

Most common adverse reactions (>30%) by SC route are: nausea, anemia, thrombocytopenia, vomiting, pyrexia, leukopenia, diarrhea, injection site erythema, constipation, neutropenia and ecchymosis. Most common adverse reactions by IV route also included petechiae, rigors, weakness and hypokalemia. Azacitidine is available in lyophilized powder in 100 mg single-use vials.

Azacitidine is rapidly absorbed and eliminated after SC administration with the peak plasma azacitidine concentration occurring in 0.5 hour and a mean half-life of 41 minutes. The bioavailability of SC azacitidine relative to IV azacitidine is approximately 89%, based on AUC. AUC and C_{max} of SC administration of azacitidine were approximately dose proportional within the 25 to 100 mg/m² dose range. Multiple dosing at the recommended dose-regimen does not result in drug accumulation. Urinary excretion is the primary route of elimination of azacitidine and its metabolites [[Vidaza Prescribing Information 2015](#)].

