| 1. To evaluate clinical activity after treatment with GSK2879552, alone or in combination with azacitidine, in adult subjects with HR MDS previously treated with HMA. | 1. Clinical benefit rate (CBR) defined as % of subjects achieving CR, mCR, PR, cytogenetic response, HI or SD. Objective response rate (ORR) defined as % of subjects achieving CR, mCR, PR, cytogenetic response, or HI [as per 2006 IWG criteria]). |
| Secondary | |
| 1. To further evaluate the safety and tolerability of GSK2879552 administered alone or in combination with azacitidine. | 1. Changes in safety parameters: e.g. AEs and SAEs, changes in laboratory values, vital signs, electrocardiograms [ECGs], and physical examinations. |
| 2. To characterize the population PK of GSK2879552, alone or in combination with azacitidine in patients with HR MDS previously treated with HMA. | 2. Population PK parameters for GSK2879552 such as clearance (CL/F). |
| 3. To evaluate duration of response, duration of clinical benefit, progression-free survival, and overall survival. | 3. Duration of response (DOR) defined as the time from first documented response to disease progression. Progression free survival (PFS) defined as the time from first dosing day to disease progression or death from any cause. Overall survival (OS) defined as the time from first dosing day until death from any cause. |
| 4. To evaluate frequency and time to progression to AML (per 2006 IWG criteria) | 4. Proportion of subjects with disease progression to AML. Time to AML progression. |
| 5. To evaluate platelet and RBC transfusion dependence. | 5. Number of documented platelet and RBC transfusions per month within 3 months prior to study entry and while on study. |

| Objectives | Endpoints |
|---|--|
| Exploratory | |

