9.4. Key Elements of Analysis Plan

Data will be listed and summarized according to the GSK reporting standards, where applicable. Data will be listed and summarized mostly by doses. Separate analyses will be provided for Part I and in Part II where applicable. In some instances, analysis may also be generated based on the dose of GSK2879552. Data from Part I and Part II may be combined for some analyses at the end of the trial, for subjects treated at the same dose level. Complete details will be documented in the Reporting and Analysis Plan (RAP). Any deviations from, or additions to, the original analysis plan described in this protocol will be documented in the RAP and final study report.

As it is anticipated that accrual will be spread thinly across centers and summaries of data by center would unlikely be informative, therefore data from all participating centers will be pooled prior to analysis.

All data up to the time of study completion/withdrawal from study will be included in the analysis, regardless of duration of treatment.

As the duration of treatment for a given subject will depend on efficacy and tolerability, the duration of follow-up will vary between subjects. Consequently there will be no imputation for missing data.

Demographic and baseline characteristics will be summarized.

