9.4.1. Clinical Activity Analyses

The clinical benefit rate (CBR) is defined as the percentage of subjects with a Complete Remission (CR), marrow complete remission (mCR) or a Partial Remission (PR) or a Hematologic Improvement (HI) or Stable Disease (SD) at any time as per disease-specific criteria ([Appendix 5](#) and [Appendix 6](#)). Subjects with unknown or missing response will be treated as non-responders, i.e. these subjects will be included in the denominator when calculating the percentage. The number and types of responses, as outlined in IWG criteria [[Cheson, 2006](#)], will be listed and summarized separately, as appropriate.

The ORR will be reported at the interim and final analysis for each arm specified in Part 2 as well as all evaluable subjects in Part 1 treated at or above RP2D. Part 1 and Part 2 subjects who received the same dose within the same treatment arm may be combined together in the analysis. The estimates along with 95% exact confidence interval (CI) will be provided.

The CBR and ORR differences between the two cohorts will be provided along with corresponding 95% CI. A chi-square test will be used to test for differences between arms if data warrant.

Duration of response is defined as the subset of subjects who show a response (CR, mCR, PR, or HI), the time from first documented evidence of response until the first documented sign of disease progression or death. Duration of response will be summarized descriptively for each arm, if data warrant, using Kaplan-Meier medians and quartiles. Details on rules for censoring will be provided in the RAP.

For the analysis of **Progression-free survival (PFS)**, if the subject received subsequent anti-cancer therapy prior to the date of documented events, PFS will be censored at the last adequate assessment (e.g. assessment where visit level response is CR, mCR, PR, HI or SD) prior to the initiation of therapy. Progressive disease (PD) will also be defined per standard criteria. Otherwise, if the subject does not have a documented date of events, PFS will be censored at the date of the last adequate assessment. Further details on rules for censoring will be provided in the RAP. PFS will be summarized by arm and dose using Kaplan-Meier quantile estimates along with 2-sided 95% CIs at the time of final analysis, if data warrant.

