12.10. Appendix 10: IWG CRITERIA FOR RESPONSE

| Category | Response Criteria |
|------------------------------|--|
| Complete Remission | Bone marrow: $\leq 5\%$ myeloblasts with normal maturation of all cell linesa Persistent dysplasia will be noteda,b Peripheral blood (Response must be maintained for at least 4 weeks) Hgb ≥ 11 g/dL Platelets ≥ 100 Gi/L Neutrophils ≥ 1.0 Gi/Lb Blasts 0% |
| Partial Remission | All CR criteria if abnormal before treatment except: Bone marrow blasts decreased by $\geq 50\%$ over pre-treatment but still $> 5\%$ Cellularity and morphology not relevant |
| Marrow CR^b | Bone marrow: $\leq 5\%$ myeloblasts and decrease by $\geq 50\%$ over pre-treatment ^b Peripheral blood: if HI responses, they will be noted in addition to marrow CR ^b |
| HI | Erythroid (HI-E): hgb increase of > 1.5 g/dL decrease of $>$ RBC transfusions/8weeks versus pretreatment requirement in previous 8 weeks; only RBC transfusions given for a pretreatment Hgb of < 9.0 g/dL count Platelet (HI-P): increase of $> 30,000$ /mL (starting with $> 20,000$ /mL) increase from $< 20,000$ /mL to $> 20,000$ /mL by $> 100\%$ Neutrophil (HI-N): increase of $> 100\%$ and > 500 /uL |
| Stable Disease | Failure to achieve at least PR, but no evidence of progression > 8 wks |
| Disease Progression | For subjects with: 
 • Less than 5% BM blasts: $\geq 50\%$ increase in blasts to $> 5\%$ blasts • 5%-<10% BM blasts: $\geq 50\%$ increase to $> 10\%$ blasts • 10%-<20% BM blasts: $\geq 50\%$ increase to $> 20\%$ blasts • 20%-30% BM blasts: $\geq 50\%$ increase to $> 30\%$ blasts Any of the following: 
 • At least 50% decrement from maximum remission/response in granulocytes or platelets • Reduction in Hgb by ≥ 2 g/dL • Transfusion dependence |
| Non-evaluable | Subject does not meet any of the above criteria |

BM = bone marrow ; CR = complete remission; Hgb = hemoglobin;; PR = partial remission

a. Dysplastic changes should consider the normal range of dysplastic changes (modification).

b. Modification to IWG response criteria [[Cheson, 2006](#)].

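### The final-analysis trigger in protocol section 5.6 sets no minimum follow-up, so a recent progression-free enrolee can be scored a clinical-benefit failure by the calendar alone

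*Protocol*

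**What the plan says.** - **Trigger (section 5.6).** The study is "considered completed for the purpose of a final analysis when 70% of subjects enrolled in Part 2 have progressed or died". No other condition is attached.
- **Endpoint (section 3.2).** "Clinical benefit rate (CBR) defined as % of subjects achieving CR, mCR, PR, cytogenetic response, HI or SD". Section 9.1.2 tests this rate in each arm, 30% against 50%, and rejects the null with at least 12 of 28.
- **SD (Appendix 10).** "Failure to achieve at least PR, but no evidence of progression > 8 wks". The non-evaluable category is: "Subject does not meet any of the above criteria".
- **Unknown response (section 9.4.1).** "Subjects with unknown or missing response will be treated as non-responders", and they stay in the denominator.
- **Data included (section 9.4).** "All data up to the time of study completion/withdrawal from study will be included in the analysis, regardless of duration of treatment". Section 9.3.1 evaluates clinical activity in everyone who received at least one dose.

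**The concern.** The trigger suits a time-to-event endpoint, but it is attached to a proportion whose most easily reached success category needs a fixed observation time. Read together, these rules take a subject dosed a few weeks before the cut-off, still progression-free but with no response or hematologic improvement, and count that subject as a failure. The only reason is the date.

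Each arm needs 12 successes in 28, so a few such subjects can decide the outcome. The risk is that an active arm is dropped.

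**Working it through.** **1. The plan's own figures.** An exact binomial recursion through the Table 5 futility boundaries (sample size/stop at or below: 10/1, 12/2, 14/3, 16/3, 18/4, 20/5, 22/6, 24/8, 26/9), with success at 12 or more of 28, gives type I error 0.0991 at CBR 0.30 and power 0.8174 at CBR 0.50. The protocol states 0.099 and 81%. Without futility stopping, P(X ≥ 12 | 28, 0.30) = 0.1028 and P(X ≥ 12 | 28, 0.50) = 0.8275. The last figure is the reference for step 4.

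**2. The trigger.** 0.70 × 56 = 39.2, so the 40th progression or death. Up to 56 − 40 = 16 subjects are then event-free.

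**3. CBR and PFS are linked.** Anyone progression-free beyond 8 weeks is at least SD, so apart from missing assessments CBR ≥ S(8 weeks). Eight weeks is 56/30.4 = 1.84 months. With exponential PFS of median m months, S = exp(−ln 2 × 1.84/m):

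- m = 1.84: 0.50
- m = 2: 0.53
- m = 3: 0.65
- m = 4: 0.73

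At the powered alternative (CBR 0.50), no more than about half the subjects can be progression-free past 8 weeks. Any power calculation at 0.50 has to respect this.

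**4. Power at CBR 0.50 under the trigger.** Accrual and PFS are not in the protocol (section 2.1.2 gives only historical median OS of 5.6 and 4.3 months), so these are assumptions:

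- 56 subjects, 1:1, uniform accrual
- half progression-free past 8 weeks
- all benefit through SD, which is the upper bound on the loss
- cut at the 40th event but not before the last enrolment
- no futility stopping, Part 1 subjects not pooled

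With full follow-up, power is about 0.83. Under the trigger:

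| PFS shape | Accrual 6 mo | 12 mo | 18 mo | 24 mo |
|---|---|---|---|---|
| Exponential, median 8 weeks | 0.53 | 0.52 | 0.62 | 0.67 |
| Half progress by 8 weeks, rest with a further median of 4 months | 0.76 | 0.63 | 0.62 | 0.68 |
| Half progress by 8 weeks, rest with a further median of 8 months | 0.83 | 0.77 | 0.71 | 0.69 |

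Repeat runs move a cell by about 0.01, so the range is about 0.53 to 0.82.

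**5. The same loss by count.** With the exact recursion at CBR 0.50, let the last k subjects per arm be unable to score SD. The first power figure takes SD as all of the benefit, the second as half of it.

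| k per arm | Power |
|---|---|
| 0 | 0.817 |
| 1 | 0.774-0.796 |
| 2 | 0.718-0.771 |
| 3 | 0.654-0.743 |
| 4 | 0.580-0.714 |

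At k = 3, type I error is 0.044-0.070, below the planned 0.099.

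**6. Where it does little.** At exponential median 3 months, true CBR is at least 0.654. P(X ≥ 12) is then 0.996 for 28 subjects and 0.977 for 25 (three lost per arm). Over accrual of 6-30 months and median PFS of 2-8 months, the mean number of event-free subjects with 8 weeks or less of follow-up at the trigger runs from 0 to 6.8, both arms together. In 11 of those 25 scenarios it is at most one.

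**The case against.** **The loss may be small.** This stands in part. If median PFS is 3 months or more, CBR is well above 0.50 and power stays high. It is tempting to combine a median of 3 months with CBR 0.50 and report a large loss, but Appendix 10 makes the two incompatible under exponential PFS. The large losses arise when CBR is near the 0.50 for which the trial is powered.

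**Late enrolees can still succeed.** True: CR, mCR, PR, cytogenetic response or HI can be reached within 8 weeks, and assessments are every 4 weeks. Only SD is lost, so the step 4 figures are an upper bound.

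**Part 1 subjects are analysed with Part 2.** Section 9.1.2 pools those with the same starting dose. They enrol first and have the longest follow-up, so pooling would dilute the loss. The calculation leaves them out.

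**Section 9.4.1 mentions a visit-level response of SD.** It does so in the PFS censoring rule. If an SD call before 8 weeks counted towards CBR, it would contradict Appendix 10, so it does not settle the matter.

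**Cut-off details belong in the analysis plan.** The trigger and the non-responder rule are both fixed in the protocol. What section 9.4.1 specifically defers is the censoring rules for DOR, PFS and OS.

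**A reader might infer that the analysis will run before all 56 are enrolled.** Section 5.6 does not exclude this, nor say whether its denominator is the planned 56 or those enrolled to date. But section 9.1.2 says an arm not stopped for futility continues to its target size, so the step 4 figures assume full enrolment.

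**Conclusion.** The point holds. Following sections 5.6 and 9.4.1 and Appendix 10 as written can count recent progression-free subjects as CBR failures. The error is downward only: the observed CBR and the power fall, and no false-positive risk is created.

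The size is conditional. On the assumptions of step 4, power falls from about 0.83 to about 0.53-0.82. It is negligible with fast accrual and a long PFS tail, and small if median PFS (exponential) is 3 months or more. The documents therefore do not support a flat statement that power will fall below 81%.

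Nor do they support a minimum of six cycles for every subject. Section 2.2.6 reports for azacitidine that "the median number of cycles to first response was three, with 90 percent of responses seen by cycle six", from which a reader might infer that six cycles are needed. But a subject unprogressed after 8 weeks is already a CBR success through SD. Later responses can change only ORR, which has no success threshold.

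**What to change.** Amend section 5.6 so that the final analysis takes place when all three conditions hold:

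1. Part 2 enrolment is complete, or the arm has been stopped.
2. 70% of Part 2 subjects have progressed or died.
3. Every treated Part 2 subject has progressed, died, withdrawn, or had the first disease assessment after 8 weeks.

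The third condition should refer to the first assessment after 8 weeks rather than to Cycle 3 Day 1. That visit falls exactly 2 × 28 = 56 days after first dosing, with a window of 3 days either way, so it can come too early for Appendix 10.

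The cost is one sentence and no extra subjects. With assessments every 4 weeks, the last enrolee meets the condition at about 8 to 12 weeks, so the delay is at most about 2-3 months after the last enrolment. There is none where the 70% condition is reached later than that.
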